Uterovaginal Prolapse	Genitourinary	5,585	11,170	16,755	22,340	27,925
Postmenopausal Bleeding	Genitourinary	4,055	8,110	12,165	16,220	20,275
Urolithiasis	Genitourinary	3,750	7,500	11,250	15,000	18,750
Obstructive and reflux uropathy	Genitourinary	2,350	4,700	7,050	9,400	11,750
Neuropathic Bladder	Genitourinary	2,330	4,660	6,990	9,320	11,650
Glomerulonephritis	Genitourinary	1,800	3,600	5,400	7,200	9,000
Postcoital Bleeding	Genitourinary	1,580	3,160	4,740	6,320	7,900
Dysmenorrhoea	Genitourinary	1,475	2,950	4,425	5,900	7,375
Endometriosis	Genitourinary	1,250	2,500	3,750	5,000	6,250
End Stage Renal Disease	Genitourinary	950	1,900	2,850	3,800	4,750
Hydrocele	Genitourinary	925	1,850	2,775	3,700	4,625
Endometrial Hyperplasia	Genitourinary	760	1,520	2,280	3,040	3,800
Female Infertility	Genitourinary	730	1,460	2,190	2,920	3,650
Tubulo-interstitial Nephropathy	Genitourinary	700	1,400	2,100	2,800	3,500
Chronic Cystitis	Genitourinary	530	1,060	1,590	2,120	2,650
Male infertility	Genitourinary	250	500	750	1,000	1,250
Anaemia – other	Haem/Imm	13,030	26,060	39,090	52,120	65,150
Iron Deficiency Anaemia	Haem/Imm	9,520	19,040	28,560	38,080	47,600
Agranulocytosis	Haem/Imm	2,230	4,460	6,690	8,920	11,150
Secondary Thrombocytopaenia	Haem/Imm	1,470	2,940	4,410	5,880	7,350
Vitamin B12 deficiency anaemia	Haem/Imm	1,030	2,060	3,090	4,120	5,150
Hypersplenism	Haem/Imm	500	1,000	1,500	2,000	2,500
Aplastic Anaemia	Haem/Imm	490	980	1,470	1,960	2,450
Folate Deficiency Anaemia	Haem/Imm	480	960	1,440	1,920	2,400

Secondary Polycythaemia	Haem/Imm	320	640	960	1,280	1,600
Primary thrombocytopenia	Haem/Imm	250	500	750	1,000	1,250
Hyposplenism	Haem/Imm	200	400	600	800	1,000
Sarcoidosis	Haem/Imm	200	400	600	800	1,000
Thrombophilia	Haem/Imm	200	400	600	800	1,000
Other haemolytic anaemia	Haem/Imm	110	220	330	440	550
Immunodeficiency	Haem/Imm	90	180	270	360	450
Sickle Cell Trait	Haem/Imm	60	120	180	240	300
Thalassaemia Trait	Haem/Imm	40	80	120	160	200
Bacterial Infection	Infections	24,590	49,180	73,770	98,360	122,950
Infection – Other organisms	Infections	23,180	46,360	69,540	92,720	115,900
Infection – Lower Respiratory Tract	Infections	18,680	37,360	56,040	74,720	93,400
Urinary Tract Infection	Infections	12,360	24,720	37,080	49,440	61,800
Infection – Digestive System	Infections	8,790	17,580	26,370	35,160	43,950
Infection – Skin	Infections	7,040	14,080	21,120	28,160	35,200
Infection – Other organs	Infections	5,370	10,740	16,110	21,480	26,850
Septicaemia	Infections	4,800	9,600	14,400	19,200	24,000

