If you are currently taking the pill, select 'Still taking the pill'. If you are unsure, please provide an estimate or select 'Do not know'.

[FH6 (UKB)]

Have you **ever** used hormone replacement therapy (HRT)?

SELECT one of 4 from

1 Yes

0 No -> **GO TO FH9**

-1 Do not know -> **GO TO FH9**

-3 Prefer not to answer -> **GO TO FH9**

[FH6A (UKB)]

How old were you when you first used HRT?

Enter INTEGER

[Require \geq 16, \leq current age]

OR

-1 Do not know

OR

-3 Prefer not to answer

If you are unsure, please provide an estimate or select 'Do not know'.

[FH6B (UKB)]

How old were you when you last used HRT?

Enter INTEGER

[Require \geq FH6A, \leq current age]

OR

-1 Do not know

OR

-11 Still taking HRT

OR

-3 Prefer not to answer

If you are currently using HRT, select 'Still taking HRT'.

If you are unsure, please provide an estimate or select 'Do not know'.

[FH9 (UKB)]

Have you had a hysterectomy (womb removed)?

SELECT one of 4 from

1 Yes

0 No -> GO TO FH10

-5 Not sure -> GO TO FH10

-3 Prefer not to answer -> GO TO FH1

[FH9A (UKB)]

How old were you when you had your hysterectomy?

Enter INTEGER

[Require \geq 0, \leq current age]

OR

-1 Do not know

OR

-3 Prefer not to answer

If you are unsure, please provide an estimate or select 'Do not know'.

[FH10 (UKB)]

Have you had BOTH ovaries removed?

SELECT one of 4 from

1 Yes

0 No -> GO TO L1(UKB)

-5 Not sure -> GO TO L1(UKB)

-3 Prefer not to answer -> GO TO L1(UKB)

Only enter 'Yes' if you have had both ovaries removed

If you are unsure of whether both ovaries have been removed, select 'Do not know'.

[FH10A (UKB)]

How old were you when you had BOTH ovaries removed?

Enter INTEGER

[Require ≥ 0 , \leq current age]

OR

-1 Do not know

OR

-3 Prefer not to answer

[L1 (UKB)]

Have you ever been diagnosed with any of the following by a doctor or other health professional?

Please select all that apply

We will ask more details for any type of disorder that you select here

TOGGLE

[Require ≥ 1 choices]

- 6 Autoimmune disorder -> **GO TO AUTO_A**
- 7 Blood disorders (Anaemia) -> **GO TO BLOOD_A**
- 2 Cancer -> **GO TO CANC_A**
- 3 Complications or difficulties in pregnancy or childbirth -> **SHOW IF FEMALE; GO TO PREG_A**
- 4 Digestive system or liver problems -> **GO TO DIG_A**
- 5 Endocrine, nutritional and metabolic disorders (e.g., diabetes, thyroid disorder, vitamin deficiencies) -> **GO TO EN_A**
- 6 Eye or visual problems -> **GO TO EYE_A**

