- 7 Fractures, breaks, or joint problems -> **GO TO FRAC_A**
- 8 Heart or circulatory disease (e.g. high blood pressure or stroke) -> **GO TO HEART_A**
- 9 Kidney or urinary system disorders -> **GO TO KIDN_A**
- 10 Lung or respiratory problems -> **GO TO LUNG_A**
- 11 Mental health conditions (e.g. depression, bipolar disorder) -> **GO TO MH_A**
- 12 Neurodevelopmental conditions (e.g., Autism spectrum disorder, ADHD) -> **GO TO ND_A**
- 13 Neurological disorders (things that affect that brain or nervous system) -> **GO TO NEU_A**
- 14 Reproductive system problems -> **GO TO REPRO_A**
- 15 Other not listed -> **GO TO L5DF**
- 16 None of these -> **GO TO L5DF**
- 1 I don't know **[EXCLUSIVE]** -> **GO TO L5DF**
- 3 Prefer not to answer **[EXCLUSIVE]** -> **GO TO L5DF**

If the diagnosis was for cancer, please select cancer. We will ask more about the type of cancer in a subsequent question.

[AUTO_A]

Have you ever been diagnosed with any of the following autoimmune disorders by a doctor or other health professional?

- 0 Rheumatoid arthritis
- 1 Lupus
- 2 Inflammatory Bowel Disease (IBD)
- 3 Multiple Sclerosis (MS)
- 4 Graves' disease
- 5 Guillain-Barre syndrome
- 6 Psoriasis
- 7 Other (not listed)
- 1 I don't know
- 3 Prefer not to answer

[BLOOD_A]

Have you ever been diagnosed with any of the following types of anaemia by a doctor or other health professional?

- 0 Iron deficiency anaemia
- 1 Vitamin deficiency anaemia
- 2 Sickle cell anaemia
- 3 Aplastic anaemia
- 4 Thalassemia
- 5 Other (not listed)
- 1 I don't know
- 3 Prefer not to answer

[CANC_A (CONNECT)]

Which type(s) of cancer specifically were you diagnosed with?

Please indicate where the cancer originated, even if it spread to other body areas

- 0 Anal
- 1 Bladder
- 2 Brain
- 3 Breast
- 4 Cervical
- 5 Colon/rectal
- 6 Oesophageal

- 7 Head and neck (Including cancers of the mouth, sinuses, nose, or throat. Not including brain or skin cancers.)
- 8 Gastric
- 9 Kidney
- 10 Leukaemia (blood and bone marrow)
- 11 Liver
- 12 Lung or bronchial
- 14 Lymphoma
- 15 Ovarian
- 16 Pancreatic
- 17 Prostate
- 18 Skin
- 19 Stomach
- 20 Testicular
- 21 Thyroid
- 22 Uterine (endometrial)
- 23 Another type of cancer
- 24 I know I had cancer, but don't know what type
- 1 I don't know
- 3 Prefer not to answer

[CANC_B (CONNECT)]

What type of skin cancer specifically were you diagnosed with?

- 9 Melanoma
- 10 Basal cell
- 11 Squamous cell
- 1 I don't know
- 3 Prefer not to answer

[PREG_A (CONNECT+ICD)]

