What type of complication or difficulties with pregnancy or childbirth have you experienced?

- 0 Miscarriage (pregnancy loss before 20 weeks)
- 1 Stillbirth (pregnancy loss after 20 weeks)
- 2 Live birth and still birth (loss of one or more multiples)
- 3 Ectopic or tubal pregnancy
- 4 Trying to get pregnant for more than a year but not getting pregnant during that time
- 5 hyperemesis gravidarum
- 6 Gestational diabetes
- 7 Preterm labour and delivery
- 8 Complicated labour and delivery
- 9 Traumatic labour or delivery
- 10 Pre-eclampsia

- 11 Eclampsia
- 12 Gestational hypertension
- 13 Other (not listed)
- 1 I don't know
- 3 Prefer not to answer

[DIG_A (CONNECT)]

Have you ever been diagnosed with any of the following digestive system problems by a doctor or other health professional?

- 0 Gastro-oesophageal Acid Reflux (GORD)
- 1 Barrett's Oesophagus
- 2 Irritable bowel syndrome
- 3 Inflammatory Bowel Disease
- 4 Diverticulitis or Diverticulosis
- 5 Ulcerative Colitis
- 6 Crohn's Disease
- 7 Coeliac Disease (also known as Gluten-Sensitive Enteropathy)
- 8 Gallstones (Biliary Stones)
- 9 Fatty liver disease
- 10 Liver Cirrhosis
- 11 Hepatitis
- 12 Pancreatitis
- 5 Other (not listed)
- 1 I don't know
- 3 Prefer not to answer

[EN_A]

Have you ever been diagnosed with the following conditions by a doctor or health professional?

- 0 Type 1 diabetes
- 1 Type 2 diabetes
- 2 overactive thyroid
- 3 underactive thyroid
- 4 Cushing syndrome
- 5 Lactose intolerance
- 6 Vitamin A deficiency
- 7 Thiamine deficiency
- 8 Vitamin D deficiency
- 3 Other (not listed)
- 1 I don't know
- 3 Prefer not to answer

[EYE_A]

Have you ever been diagnosed with any of the following eye or visual problems by a doctor or other health professional?

- 3 Glaucoma
- 1 Visual impairment including blindness
- 2 Double vision
- 3 Night blindness
- 4 Colour blindness
- 5 Macular degeneration
- 6 Cataracts
- 7 Retinal detachment
- 8 Diabetic retinopathy
- 9 Other (not listed)
- 1 I don't know
- 3 Prefer not to answer

[FRAC_A]

What type of fractures, breaks, joint or bone problems have you experienced?

- 45 Hip fracture
- 1 Osteoporosis
- 2 Osteoarthritis (arthritis)
- 3 Gout
- 4 Other (not listed)
- 1 I don't know
- 3 Prefer not to answer

[HEART_A (CONNECT)]

Have you ever been diagnosed with any of the following heart or circulatory diseases by a doctor or other health professional?

- 0 B-12 Deficiency (Pernicious Anaemia)
- 1 Coronary Artery/Coronary Heart Disease

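### B-12 deficiency (pernicious anaemia) is named only in the heart-disease list of the baseline questionnaire, so named reports coincide with the heart/circulatory tick by construction

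*Protocol*

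**What the plan says.** Appendix E asks about diagnoses in two steps. A gate question (L1 for the participant, Y13D for the father, Y16D for the mother, Y19 for siblings) lists broad categories, of which several may be ticked. Each ticked category opens its own list.

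- The gate "Heart or circulatory disease (e.g. high blood pressure or stroke" opens HEART_A, which asks "Have you ever been diagnosed with any of the following heart or circulatory diseases by a doctor or other health professional". Its first response (code 0) is "B-12 Deficiency (Pernicious Anaemia". The same response is code 0 of HEART_A_DAD, HEART_A_MOM and HEART_A_SIB.
- The gate "Blood disorders (Anaemia" opens BLOOD_A, which asks "Have you ever been diagnosed with any of the following types of anaemia by a doctor or other health professional". It offers "Vitamin deficiency anaemia" and an unlisted-other response. Neither B-12 nor pernicious anaemia is named there. The relatives' versions match.
- The gate "Endocrine, nutritional and metabolic disorders (e.g., diabetes, thyroid disorder, vitamin deficiencies" opens EN_A. This names vitamin A, thiamine and vitamin D, but not B-12, plus unlisted other.
- The autoimmune gate opens AUTO_A, where only unlisted other would fit.

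Appendix A lists "Vitamin B12 deficiency anaemia" in the Haem/Imm category, with 1,030 expected incident diagnoses per million over 2.5 years.

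**The concern.** A blood disorder sits in a cardiovascular list, against the protocol's own classification. A person with B-12 deficiency would naturally tick blood disorders, or the nutritional category whose gate mentions vitamin deficiencies. Neither route leads to the named option. Only those who also tick the heart/circulatory category see it.

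Two things are at stake. The specific diagnosis will be under-recorded. How often it is recorded will also depend on whether the respondent ticked the heart/circulatory category, so a self-report analysis of B-12 deficiency against cardiovascular history would carry an association created by the questionnaire. The cohort is large enough for such an association to look like a finding. Table 2 gives a minimum detectable odds ratio of 1.09 for 5,000 cases, 25% exposure prevalence and a critical p-value of 0.05.

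**Working it through.** The plan states no figure on this point, so there is nothing to reproduce. The check is a routing trace followed by an illustrative calculation.

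**Routing for the participant; the relatives' blocks follow the same pattern**

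| Gate ticked | List opened | How B-12 deficiency can be recorded |
|---|---|---|
| Heart or circulatory | HEART_A | By name |
| Blood disorders | BLOOD_A | Generic vitamin deficiency anaemia, or other |
| Endocrine/nutritional | EN_A | Other only |
| Autoimmune | AUTO_A | Other only |

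There is one route to the named option. Every record with code 0 in HEART_A therefore also has the heart/circulatory tick. Among people without that tick, the named option is never recorded.

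**Does pooling with the generic anaemia option cure it?**

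All inputs here are assumptions; the protocol gives none of them.

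- Prevalence of B-12 deficiency is 2%, independent of the heart/circulatory tick.
- A share b of cases tick blood disorders, whether or not they tick heart/circulatory, and all of those choose the vitamin option. Values tried: b = 0.4, 0.6, 0.8.
- 90% of cases shown the named option select it.

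Probability that a case is recorded by either route:

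- heart/circulatory ticked: 1 − (1 − b) × 0.1
- not ticked: b

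Multiplying by 0.02 gives the recorded prevalence in each group, p1 (ticked) and p0 (not ticked). The odds ratio is [p1/(1 − p1)] / [p0/(1 − p0)].

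| b | Recorded, ticked | Recorded, not ticked | p1 | p0 | Odds ratio |
|---|---|---|---|---|---|
| 0.4 | 0.94 | 0.40 | 0.0188 | 0.0080 | 2.38 |
| 0.6 | 0.96 | 0.60 | 0.0192 | 0.0120 | 1.61 |
| 0.8 | 0.98 | 0.80 | 0.0196 | 0.0160 | 1.23 |

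The true odds ratio in this set-up is 1.

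**Total capture by any route**

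Let h be the share ticking heart/circulatory, assumed 0.2 to 0.4. Capture is h × [1 − (1 − b) × 0.1] + (1 − h) × b.

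- h = 0.2, b = 0.4: 0.2 × 0.94 + 0.8 × 0.40 = 0.508
- h = 0.4, b = 0.8: 0.4 × 0.98 + 0.6 × 0.80 = 0.872

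About 51% to 87% of cases are recorded in some form. What is lost is mainly the specific diagnosis and equal ascertainment between the two groups.

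**The case against.** Much of the case on the other side stands, and it rules out several stronger readings.

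- A reader might infer that nobody can report the condition without first ticking heart disease. The documents do not support this: the gate is multi-select, and BLOOD_A and its relatives' versions offer the generic vitamin option.
- A reader might infer that only 18% to 36% of cases are captured (0.9 × 0.2 to 0.9 × 0.4). That counts the named option alone. Total capture on the same assumptions is the 51% to 87% shown above.
- A reader might infer an infinite odds ratio with heart disease. That holds only for the named option against the gate tick. HEART_A also lists high cholesterol and hypertension, and a respondent may tick the gate and select nothing but B-12. Against a specific diagnosis such as myocardial infarction or stroke, the odds ratio would be inflated but finite. An analysis restricted to people shown HEART_A avoids the gate artefact.
- A reader might extend the point to multiple sclerosis and rheumatoid arthritis, which are named only in AUTO_A. Both sit under a correct heading there, so listing them elsewhere as well is a preference.

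The strongest objection is linkage. Sections 2.6 and 5.1 plan to take participants' diagnoses from primary and secondary care records, and Section 3.6 aims the questionnaire at what linkage cannot supply. Appendix A's B-12 count itself comes from coded records. This largely answers the point for participants. It does not answer it for fathers, mothers and siblings, because no linkage to relatives' records is described and the questionnaire is the only stated source of their history.

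The condition is also uncommon: 1,030 incident diagnoses per million is about 0.1% over 2.5 years. That limits the number of people affected, not the direction of the bias.

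**Conclusion.** The option is misplaced in all four blocks. B-12 deficiency (pernicious anaemia) is named only behind the heart/circulatory tick and can otherwise be recorded only non-specifically. Named reports coincide with that tick by construction, which follows from the routing and needs no assumption.

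The size of the bias after pooling, an odds ratio of about 1.2 to 2.4, rests wholly on assumed inputs: 80% to 40% of cases ticking blood disorders, 90% reporting when shown, 2% prevalence, and independence of the condition from the tick. Pooling also mixes in other vitamin deficiency anaemias. Linkage should contain the problem for participants; family history remains exposed. This is a questionnaire fault worth correcting, with no bearing on the programme's sample size or main aims.

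**What to change.** Move the B-12 (pernicious anaemia) option from HEART_A to BLOOD_A in the self, father, mother and sibling blocks. Reword the existing BLOOD_A vitamin option to *Other vitamin deficiency anaemia (e.g. folate)* so that the two do not overlap. Listing the option in both places would not do, because heart tickers would keep their second chance to report.

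Under the assumptions above, both groups would then be recorded with probability b, so the spurious odds ratio becomes 1. The second chance for heart tickers goes: capture by any route falls from 0.508 to 0.40 at the low end and from 0.872 to 0.80 at the high end, but those reports now carry the specific diagnosis. The remaining cost is small: one response option moved and one reworded in four blocks of a digital questionnaire. Pilot responses to these items stay under the old layout and should be flagged as such. The short questionnaire in Section 3.7 draws on these items, so the change is best made before its items are chosen.

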Appendix E: Baseline
Questionnaire

KEY	2
ABOUT YOU AND YOUR HOUSEHOLD [SECTION 1]	2
WORK AND EDUCATION [SECTION 2]	12
YOUR LIFESTYLE [SECTION 3]	18
FAMILY HEALTH HISTORY [SECTION 4]	43
YOUR HEALTH HISTORY [SECTION 5]	70

Key

[Anything in square brackets is not shown to participants]
[CAPITAL SQUARE BRACKETS INDICATE VARIABLE NAME (BRACKETED TEXT INDICATES QUESTION SOURCE)]

Text in square boxes indicates help text

About you and your household [SECTION 1]

[SECTION INTRO]

This section is where we gather most of our data.

This is the information that will help researchers make discoveries to improve the health of people in the UK. It will be the largest and most diverse research project that has been done in the UK. We are grateful that you and many others are donating their information to help future generations live in good health for longer.

[INTRO1D(UKB)]

If you do not wish to answer a question you can select 'Prefer not to answer'.

If you want to see previous questions and change your answers, use the BACK button.

If you have any difficulties with completing this, you can use the HELP button or ask a staff member for assistance.

Remember, if you cannot find an exact answer, please select the closest response.

- Please touch NEXT to continue

(H3) How to complete the questionnaires or get help

- If you do not wish to answer a question you can select 'Prefer not to answer'.
- If you want to see previous questions and change your answers, use the BACK button
- If you have any difficulties with completing this, you can use the Help button on the top right of every page.
- Remember, if you cannot find an exact answer, please select the closest response
- You can complete all the questions for each section now or save your progress and continue at a later time

The HELP button will provide you with some additional information to help you answer each question. If you still need help after reading the information provided, do not hesitate to press the HELP button.

[SEX (ONS 2021)]

What sex was assigned to you at birth?

A question about gender identity will follow later in the questionnaire

SELECT 1 from

- 1 Female
- 2 Male
- 3 Intersex
- 3 Prefer not to answer

We ask about your sex at birth because it can help researchers make new discoveries about how the sex you were born with affects health and risk of disease. It is also important when processing your biological sample in the lab

[GENDER]

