- 1 College or University degree
- 2 A levels/AS levels/BTEC or equivalent
- 3 O levels/GCSEs or equivalent
- 4 CSEs or equivalent
- 5 NVQ or HND or HNC or equivalent
- 6 Other professional qualifications e.g., nursing, teaching
- 7 None of the above **[EXCLUSIVE]**
- 3 Prefer not to answer **[EXCLUSIVE]**

A levels/AS levels and equivalent includes the Higher School Certificate O levels/GCSEs and equivalent includes the School Certificate. If your education was in another country please choose the category(ies) that best fits with your educational qualifications.

[D11 (UKB)]

At what age did you complete your continuous full-time education?

If you stopped your studies with no intention of returning, please give the age at which you stopped even if you began studying again later in life.

Enter age in years

[Require ≥ 5 , \leq current age,

Expect ≤ 40 ,

Units: years]

OR

0 Still in full time education

OR

-2 Never went to school

OR

-1 Do not know

OR

-3 Prefer not to answer

Please give the age that you completed 'continuous' full time education.

For example, if you stopped your studies when you were 17 years old with the intention that you had completed your studies but then returned to full time studies when you were 24, enter 17.

However if you only temporarily stopped your studies at 17 with the intention that you would return to studies (for instance a gap year) and then completed your full time education at 21, enter 21

[D10 (UKB)]

What is the average total income before tax received by your HOUSEHOLD?

SELECT one of 7 from

- 1 Less than £18,000
- 2 £18,000 to £30,999
- 3 £31,000 to £51,999
- 4 £52,000 to £100,000
- 5 Greater than £100,000
- 1 Do not know
- 3 Prefer not to answer

Add up the incomes of everyone in your household for your answer.

The information you provide is confidential and won't be shared with any tax authorities.

-----**END OF SECTION 2**-----

Your lifestyle [SECTION 3]

Note: square brackets are not seen

Help and hint text is presented in boxes where available

[SECTION INTRO]

In this section we ask you about your day-to-day physical activity.

This will help our researchers look at how exercise is tied to overall health, but also things like how healthy your bones, lungs, and heart as well as diseases such as type 2 diabetes.

We'll also ask about driving habits, sleep patterns and the use of tobacco, vaping and alcohol if relevant.

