- 2 Congestive Heart Failure
- 3 High Cholesterol
- 4 Heart Attack (Myocardial Infarction)
- 5 Abnormal Heart Rhythm (Arrhythmia)
- 6 Chest Pain (Angina)
- 7 Heart Valve Problems
- 8 High Blood Pressure (Hypertension) [Please do **not** include hypertension during pregnancy.]
- 9 Blood Clots (Deep Vein Thrombosis, Pulmonary Embolism)

- 10 Stroke
- 11 Other (not listed)
- 1 I don't know
- 3 Prefer not to answer

[KIDN_A (CONNECT)]

Have you ever been diagnosed with any of the following kidney or urinary tract problems by a doctor or other health professional?

- 0 Kidney stones
- 1 Chronic kidney disease (or chronic kidney failure)
- 2 Other (not listed)
- 1 I don't know
- 3 Prefer not to answer

[LUNG_A (CONNECT)]

Have you ever been diagnosed with any of the following lung or respiratory conditions by a doctor or other health professional?

- 0 Chronic Obstructive pulmonary disease, COPD (including emphysema and chronic bronchitis)
- 1 Lung fibrosis
- 2 Bronchiectasis
- 3 Asthma
- 4 Hay Fever (Allergic to pollen or Allergic Rhinitis)
- 5 Other (not listed)
- 1 I don't know
- 3 Prefer not to answer

[ND_A]

Have you ever been diagnosed with one or more of the following conditions by a professional, even if you don't have it currently? By professional we mean: any doctor, nurse, or person with specialist training.

Please include disorders even if you did not need treatment for them or if you did not agree with the diagnosis. Select ALL that apply

- 27 Autism spectrum disorder
- 28 Developmental learning disorders
- 29 Attention deficit hyperactivity disorder (ADHD)
- 30 Disorder of intellectual development
- 31 Developmental motor coordination disorder
- 32 Developmental speech or language disorders

- 33 Stereotyped movement disorder
- 34 Other (not listed)
- 35 None of the above
- 1 I don't know
- 3 Prefer not to answer

[MH_A]

Have you ever been diagnosed with one or more of the following mental health conditions by a professional, even if you don't have it currently? By professional we mean: any doctor, nurse, or person with specialist training.

Please include disorders even if you did not need treatment for them or if you did not agree with the diagnosis. Select ALL that apply

- 46 Anxiety **-> GO TO ANX_B**
- 47 Bipolar disorder
- 48 Body dysmorphia
- 49 Depression **-> GO TO DEP_B**
- 50 Premenstrual dysphoric disorder
- 51 Post Traumatic Stress Disorder
- 52 Obsessive Compulsive Disorder
- 53 Eating disorder **-> GO TO EATD_B**
- 54 Psychosis

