- 55 Schizophrenia
- 56 Schizoaffective disorder
- 57 Personality disorder
- 58 Other (not listed)
- 59 None of the above
- 1 I don't know
- 3 Prefer not to answer

[ANX_B]

Which anxiety disorder(s) specifically have you been diagnosed with in your lifetime?

- 24 Generalised anxiety disorder
- 25 Agoraphobia
- 26 Social anxiety disorder
- 27 Panic disorder
- 28 Panic attacks
- 29 Specific phobia
- 30 Other (not listed)
- 31 None of the above
- 1 I don't know
- 3 Prefer not to answer

[DEP_B]

Which depressive disorder(s) specifically have you been diagnosed with in your lifetime?

- 15 Major Depressive Disorder
- 16 Perinatal depression
- 17 Postnatal depression
- 18 Other (not listed)
- 19 None of the above
- 1 I don't know
- 3 Prefer not to answer

[EATD_B]

Which eating disorder(s) specifically have you been diagnosed with in your lifetime?

- 18 Anorexia nervosa
- 19 Atypical anorexia nervosa
- 20 Bulimia nervosa
- 21 Binge eating disorder
- 22 Other (not listed)
- 23 None of the above
- 1 I don't know
- 3 Prefer not to answer

[NEU_A]

Have you ever been diagnosed with any of the following neurological or brain disorders by a doctor or other health professional?

- 24 Epilepsy
- 25 Parkinson's disease
- 26 Alzheimer's disease/dementia
- 27 Early onset Alzheimer's disease/dementia
- 28 Vascular dementia
- 29 Migraine with aura
- 30 Migraine without aura
- 31 Other (not listed)
- 1 I don't know
- 3 Prefer not to answer

[REPRO_A (CONNECT)]

Have you ever been diagnosed with any of the following conditions by a doctor or other health professional?

- 0 Endometriosis [validation show if question refers to female]

- 1 Polycystic Ovary Syndrome (PCOS) [validation show if question refers to female]
- 2 Enlarged prostate [validation show if question refers to male]
- 3 Fibrocystic Breast, or another Benign Breast Disease (such as proliferative Benign Breast Disease or LCIS)
- 4 Ductal Carcinoma in situ (DCIS)
- 5 Uterine Fibroids
- 6 Other (not listed)
- 1 I don't know
- 3 Prefer not to answer

[L5DF]

DO YOU REGULARLY TAKE ANY OF THE FOLLOWING TYPES OF MEDICATIONS? (YOU CAN SELECT MORE THAN ONE ANSWER)

- 0 Medication for autoimmune disorders > GO TO
AUTO_MEDS_A
- 1 Medication for bone health -> GO TO
BONE_MED_A
- 2 Treatment for Cancer -> GO TO
CANC_MED_A
- 3 Medication for diabetes or diabetic health -> GO TO DIA_MED_A
- 4 Medications for Digestive problems (including acid reflux and liver problems)-
> GO TO DIG_MED_A

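### The instruction to leave out hypertension in pregnancy stands in square brackets, which the questionnaire's own Key hides from participants, so pregnancy-only hypertension can be recorded as hypertension

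*Protocol*

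**What the plan says.** The Key at the head of Appendix E sets the display convention: "Anything in square brackets is not shown to participants". It gives visible guidance a different marking: "Text in square boxes indicates help text". The introduction to Section 3 of the questionnaire repeats the first rule: "Note: square brackets are not seen".

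In Section 5, the stem of HEART_A asks "Have you ever been diagnosed with any of the following heart or circulatory diseases by a doctor or other health professional", and option 8 is "High Blood Pressure (Hypertension) [Please do not include hypertension during pregnancy". The same bracketed sentence stands in option 8 of HEART_A_MOM, HEART_A_SIB and HEART_A_DAD in Section 4.

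Pregnancy-related hypertension has its own place. PREG_A offers "Gestational hypertension" as option 12, next to pre-eclampsia and eclampsia, and PREG_A_MOM and PREG_A_SIB do the same. A participant reaches PREG_A through a separate category in L1, shown only to women. She reaches HEART_A through the heart and circulatory category.

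**The concern.** The bracketed sentence is addressed to the respondent, yet it is marked with the notation reserved for text the respondent does not see. Without it, nothing visible limits option 8 to hypertension outside pregnancy. The question covers any diagnosis at any time, and the L1 category leading to it gives high blood pressure as an example.

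The resulting error runs in one direction and enters only through women. For participants, it would tie self-reported hypertension to sex and to having had children. For family history, it would raise reported maternal hypertension relative to paternal, and it would add to the sibling item through sisters. Section 5.1 links participants to health records but not their relatives, so linkage offers no correction for the family items.

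**Working it through.** **Text comparison.**

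1. Display rule: square-bracketed text is hidden (Key, and the note opening Section 3). Visible help goes in boxes (Key).
2. Use of brackets elsewhere: they hold variable names, permitted ranges, exclusivity flags and programming conditions, for example "Endometriosis [validation show if question refers to female" in REPRO_A. That fits the Key. Exclusions meant for the respondent are elsewhere in round brackets, as in WP2 (walking), Y17 (half-brothers) and CANC_A (head and neck cancers).
3. Option 8 of the HEART_A items: a respondent-directed exclusion in square brackets. Applying step 1 removes it from view.
4. Search for a visible substitute: no stem, option or help box in L1 or HEART_A excludes pregnancy.
5. Search for a later correction: nothing prevents a respondent from ticking both HEART_A option 8 and PREG_A option 12, and no rule removes pregnancy-only cases. Ticking both does not show whether the hypertension persisted.

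**Size, for women's own reports only.** The documents give no figure for pregnancy-only hypertension, so every input below is an assumption:

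- *p*, true prevalence of chronic hypertension among the women: 5%, 10%, 20% or 30%.
- 60% of women without chronic hypertension are mothers.
- *g*, share of those mothers who had pregnancy-only hypertension: 5% to 10%.
- *t*, share of these who tick option 8: one half to all.
- Every woman with chronic hypertension ticks option 8.

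False positives = 0.60 × *g* × *t* × (1 − *p*). Share of ticks that are chronic = *p* / (*p* + false positives).

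Low case (*g* = 0.05, *t* = 0.5): 0.60 × 0.05 × 0.5 = 0.015. High case (*g* = 0.10, *t* = 1): 0.60 × 0.10 × 1 = 0.060.

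| *p* | False positives, low to high | Chronic share, low case | Chronic share, high case |
|---|---|---|---|
| 5% | 1.4 to 5.7 points | 0.05/0.0643 = 78% | 0.05/0.107 = 47% |
| 10% | 1.4 to 5.4 points | 0.10/0.1135 = 88% | 0.10/0.154 = 65% |
| 20% | 1.2 to 4.8 points | 0.20/0.212 = 94% | 0.20/0.248 = 81% |
| 30% | 1.1 to 4.2 points | 0.30/0.3105 = 97% | 0.30/0.342 = 88% |

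**Which rows are plausible.** Appendix A expects 49,730 new hypertension diagnoses per million in 2.5 years, or 49,730/1,000,000 = 5.0% of a cohort spread evenly over ages 30 to 79 and both sexes. A prevalence of ever-diagnosed hypertension of only 5% is hard to square with that rate across such a cohort. The 5% row could describe at most a young subgroup.

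**The case against.** The strongest reply is that this is a notation slip and not a known defect in the data. The sentence is phrased and emphasised for display, so a builder may well show it. Bracket use is not flawless either: the item text of PHQ9_1 opens with a stray square bracket. The note in Section 3 could be read as meaning only that the bracket marks are not seen. Section 3.6 reports cognitive testing and pilots with over 1,500 completed questionnaires. All of this stands as a reason not to claim that the live form hides the sentence, since that form is not among the documents. It does not remove the conflict. The Key refers to anything inside the brackets, the PHQ9_1 bracket is never closed, and nothing says whether the tested form displayed this sentence.

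Mitigations also count. Some women will report only through PREG_A, and records with both items ticked can be flagged for a sensitivity analysis. For participants, Section 5 makes linkage a condition of joining, Section 5.1 gives primary care diagnoses and prescriptions priority, Section 3.8 has blood pressure measured, and HEART_MED_A asks about blood pressure medication. The repair is partial: Section 2.4 itself values questionnaires for histories older than electronic records, and many older women's pregnancies will fall there. Nor does the point's importance rest on the Appendix A counts, which come from coded records and not from HEART_A.

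A reader might also infer that sister history is inflated relative to paternal history. The instrument has no sister variable for hypertension, because HEART_A_SIB asks about brothers and sisters together. Inflation of any family item also needs the respondent to know of a relative's pregnancy diagnosis and to report it under heart disease.

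**Conclusion.** The specification contradicts itself and should be corrected. Built as written, it hides an exclusion that the separate PREG_A options show was intended, so pregnancy-only hypertension can be recorded as hypertension for female participants, for mothers and in the pooled sibling item.

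Two stronger readings are not supported. One is that such cases are in fact being misrecorded: that depends on how the form was programmed and on how women divide their answers between HEART_A and PREG_A. The other is that about half of women's self-reported hypertension would be false. The 47% figure needs the lowest assumed prevalence, the highest pregnancy-only rate and every affected woman ticking the box, all together. At assumed prevalences of 20% to 30% the chronic share is 81% to 97%. The documents fix none of these inputs, and no figure is offered for mothers or siblings.

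The textual conflict is certain and the size of its effect is not. The family-history items are the more exposed part, because linkage cannot correct them.

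**What to change.** In HEART_A, HEART_A_MOM and HEART_A_SIB, take the sentence out of square brackets and put it in visible option text or a help box, for example: *Please do not include high blood pressure that occurred only during pregnancy.* The word *only* matters, because a woman whose hypertension began in pregnancy and persisted should still be counted. Delete the sentence from HEART_A_DAD. If the live form already shows it, correct the specification to match.

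The cost is a short wording change in a few items, with no new question and negligible extra completion time.
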